4 STUDY PLAN

4.1 Study Design

This is a non-randomized, prospective, open-label implementation study to determine the feasibility of establishing and integrating a PGx test into clinical care. The effectiveness aims will be assessed by comparing toxicity outcomes using a historical control group without clinical genotyping. The implementation will be deployed across cancer care sites within Penn medicine in sequential fashion, starting with PCAM followed by PPMC, and LGH.

Patients with a GI malignancy initiating chemotherapy with a fluoropyrimidine (5-FU or capecitabine) and/or irinotecan will be consented to undergo *DYPD* and *UGT1A1* genotyping, the study intervention. The PGx test order will be placed by the research coordinator and signed by the medical oncologist; a blood sample will be obtained by the phlebotomist, or saliva self-collected by the patient in clinic, and sent to CAG for genotyping. Results will be returned in the Precision Medicine tab in PennChart. For patients with an actionable genotype (variants that would require a dose adjustment of 5-FU, capecitabine or irinotecan), clinical decision support (CDS) tools will alert the ordering oncologist of the PGx result and the recommended dose adjustment. The prescribing oncologist will ultimately decide the chemotherapy dose incorporating clinical and genetic factors. The efficacy and safety of this PGx-guided approach will be determined by comparing the incidence of severe treatment related adverse events to a historical control group of GI cancer patients enrolled into PMBB.

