8 STATISTICAL PLAN

8.1 Sample size

For the implementation aims, the sample size is based on average GI oncology clinical volume and anticipated number of patients that are eligible for testing. We anticipated testing 500-800 patients during the course of the study at the three Penn Medicine sites. No hypothesis testing will be performed.

For the effectiveness aims, we hypothesize that the chemotherapy-related severe TRAEs will decrease from 60% in the variant carriers receiving full dose chemotherapy in the historical control group enrolled into the PMBB to 30% in variant carriers receiving genotype guided chemotherapy.¹⁸ The following table presents the power for different sample sizes per group and different expected proportions experiencing severe TRAEs in the PGx group, based on two-sided Fisher's exact test at the alpha level of 0.05 (Table 5). Based on the frequencies of *DPYD* and/or *UGT1A1* in the population (~10%), testing 500 patients in each group will result in ~50 patients with actionable genotypes.

Table 5. Power estimate for the reduction in Severe TRAEs with PGx testing

Toxicity rate	39% in PGx	35% in PGx	30% in PGx
N in each group with actionable variants			
18	17.8%	24.8%	35.6%
36	32.3%	45.8%	63.6%
48			80%
54	49.4%	66.3%	83.9%
70		80%	
72	67.4%	82.9%	
97	80%		

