		5. To determine if providing PGx test results will improve patient reported outcomes (PRO) during the first six cycles of chemotherapy.
Hypothesis	9	Providing clinicians with the ability to order a PGx test with a rapid turnaround time for results, along with specific dosing recommendations, will increase the utilization of PGx tests to guide pharmacotherapy decisions and improve patient drug related outcomes.

Section 3: Study Methods

Section	Index	Description
Trial design	10	Non-randomized, prospective, open-label implementation study to determine the feasibility of establishing and integrating a PGx test into clinical care.
Randomization	11	n/a
Sample size	12	No sample size calculation was performed for this feasibility study with pragmatic inclusion of eligible participants recruited over a 20- month period (Mar 2021- Dec 2022).
Interim analyses	13	No interim analyses planned
Timing of final analysis	14	Participants were followed until May 31, 2023, for toxicity assessments with an intention of 6-month follow-up for each participant. All analyses were performed collectively in May-June of 2024.
Timing of outcome assessments	15	Serial questionnaires assessing patient reported outcomes (PROs) for symptoms associated with to adverse events will be prospectively collected by the study team at the time of each treatment for the first 6 cycles.

Section 4: Statistical Principles

Section	Index	Description
Confidence intervals and p-value	16	
No hypothesis testing was performed for the primary outcome (feasibility) or secondary implementation outcomes (fidelity, penetrance).
 
Descriptive statistics (mean, SD, median, interquartile range, range, counts, and percentage) will be used to describe and compare (t-test or rank sum test for continuous variables and Fisher's exact test for categorical variables) baseline characteristics between the historical control group and PGx arms.
 
For the effectiveness aims, significance was set at an alpha=0.05.
 
No corrections were made for multiple testing. Confidence intervals pertaining to the odds of experiencing a severe TRAE were reported.

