Analysis methods	27	
1. Primary outcome: We will report the number and proportion of tests returned prior to the first dose of chemotherapy in the prospective testing arm only as this outcome was not relevant for the historical control group. The proportions were compared among clinical sites using a chi-square test. The test turn-around time was reported as median (interquartile range) and compared using the Wilcoxon rank-sum test.
 
2. Secondary outcomes:
 
 a. Fidelity- proportion of dose modifications made in agreement with the genotype guided dosing recommendations at the first dose was reported, no hypothesis testing was performed. b. Penetrance- proportion of tests orders divided by the number of patients eligible for testing based on pharmacy records indicating the number of fluoropyrimidine prescriptions during the enrollment time frame, no hypothesis testing was performed. c. Treatment-related adverse events (TRAЕ): proportion of patients experiencing a severe treatment related adverse event defined as those requiring hospitalization, visit to the emergency department, or visit to the oncology evaluation center (OEC). The proportion of patients with severe TRAEs in the prospective cohort were compared between the DPYD variant carriers vs DPYD wild-type patients. The proportion of patients with TRAEs were compared between the prospective and historical control groups among DPYD variant carriers. The proportion of patients with TRAEs in the prospective cohort were compared between the UGT1A1 poor metabolizers vs UGT1A1 normal and intermediate metabolizers. The

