		
proportion of patients with TRAEs were compared between the prospective and historical control groups among UGT1A1 poor metabolizers. Chi-square tests were used for all comparisons. Factors contributing to having a TRAE were evaluated using a multivariable logistic regression model adjusting for age, sex, race, tumor type, ECOG score, presence of metastases, intent of treatment, DPYD phenotype, and UGT1A1 phenotype using a stepwise approach.
 
 d. Relative dose intensity for fluoropyrimidines and irinotecan, defined as cumulative dose administered divided by the anticipated cumulative dose over six cycles reported as mg/m² was compared between variant carriers and wild-type patients (or PM vs. IM/NM for irinotecan) in the prospective cohort using t-tests. Relative dose intensity for fluoropyrimidines and irinotecan, was compared between the prospective and historical control groups in variant carriers (or PM for irinotecan) using t-tests. e. Patient reported outcomes (PROs) during the first six cycles of chemotherapy were compared in the prospective cohort between DPYD variant carriers and wild-type patients using chi-square tests in the subset that completed PROs. f. Patient knowledge and attitudes towards PGx testing were evaluated using chi-square and t-tests as appropriate.
Missing data	28	
 a. Prospective completion of chemotherapy related toxicity per the National Cancer Institute-Common Terminology Criteria for Adverse Events (NCI-CTCAE) was not feasible due to a lack of a consistent research coordinator throughout the study. In addition, the completion rate for the PROs was very low therefore we could not assign a grade to the adverse event. b. Revised definition severe toxicities from \geq Grade 3 toxicities to treatment related adverse events requiring treatment in the hospital, emergency department, or oncology evaluation center.

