Additional analyses	29	
 a. The number of treatment modifications (i.e., delay of treatment or dose reduction) and treatment discontinuations in the prospective cohort were compared between the DPYD variant carriers vs DPYD wild-type patients using chi-square tests. These outcomes were also compared between the prospective and historical control groups among DPYD variant carriers. These analyses were also performed for the UGT1A1 phenotype. b. Overall survival at one year was reported for the prospective and historical cohorts.
Harms	30	No harms of the genotyping intervention were reported.
Statistical software	31	SAS version 9.4 and R version 4.2.3
References	32	
 1. Henricks LM, Lunenburg CATC, De Man FM, et al. DPYD genotype-guided dose individualisation of fluoropyrimidine therapy in patients with cancer: a prospective safety analysis. The Lancet Oncology. 2018;19(11):1459-1467. doi:10.1016/S1470-2045(18)30686-7 2. Amstutz U, Henricks LM, Offer SM, et al. Clinical Pharmacogenetics Implementation Consortium (CPIC) Guideline for Dihydropyrimidine

		
Dehydrogenase Genotype and Fluoropyrimidine Dosing: 2017 Update. Clin Pharmacol Ther. 2018;103(2):210-216. doi:10.1002/cpt.911
 
3. Fresenius Kabi. Fluorouracil Prescribing Information. Food and Drug Administration. February 2024. Accessed May 1, 2024. https://www.accessdata.fda.gov/drugsatfda_docs/label/2024/040279s030lbl.pdf
 
4. Genentech. Xeloda Prescribing Information. Food and Drug Administration. December 2022. Accessed May 1, 2024. https://www.accessdata.fda.gov/drugsatfda_docs/label/2022/020896s044s045s046s047s048s049s050s051lbl.pdf
 
5. Pfizer. Camptosar Prescribing Information. Food and Drug Administration. January 2022. Accessed May 1, 2024. https://www.accessdata.fda.gov/drugsatfda_docs/label/2022/020571Orig1s053lbl.pdf

--	--	--

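### The SAP tests severe TRAE with four uncorrected contrasts at 0.05, does not say which decides effectiveness aim 4, and leaves out the pooled-carrier contrast that the protocol powered

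*Combined protocol and SAP*

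**What the plan says.** SAP item 16 (Confidence intervals and p-value) excludes feasibility, fidelity and penetrance from hypothesis testing. It then states: "For the effectiveness aims, significance was set at an alpha=0.05", followed by "No corrections were made for multiple testing". SAP item 8 defines two effectiveness aims: fewer patients with severe TRAEs (aim 4) and better patient-reported outcomes (aim 5).

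SAP item 27.2c gives four contrasts for severe TRAE:

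- DPYD carriers against DPYD wild-type, within the prospective cohort
- DPYD carriers, prospective against historical: "The proportion of patients with TRAEs were compared between the prospective and historical control groups among DPYD variant carriers"
- UGT1A1 poor metabolizers against normal and intermediate metabolizers, within the prospective cohort
- UGT1A1 poor metabolizers, prospective against historical

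On method it says "Chi-square tests were used for all comparisons". It sets no order among the four and does not say which answers aim 4.

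The protocol is more specific about direction. Section 4.1 says "The effectiveness aims will be assessed by comparing toxicity outcomes using a historical control group without clinical genotyping". Section 8.1 hypothesises that the severe TRAE rate "will decrease from 60% in the variant carriers receiving full dose chemotherapy in the historical control group" to 30% under genotype-guided dosing, and bases its power table on a "two-sided Fisher's exact test at the alpha level of 0.05". SAP item 7 also says effectiveness is judged on severe TRAE against the biobank control.

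**The concern.** Aim 4 is a single question, but the SAP offers four p-values for it, each read at 0.05. Two of them, the historical contrasts, bear directly on whether testing helped. If either may be cited as success, the 5% level does not describe the risk of a false claim. The within-cohort contrasts stand beside them with equal status, although they ask something else: whether carriers given genotype-guided treatment still differ from non-carriers.

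The documents also describe the historical contrast in three ways. Protocol 8.2.2 compares the whole PGx group with the whole control group by Fisher's exact test. Protocol 8.1 powers the comparison in carriers of DPYD and/or UGT1A1 variants together. SAP item 27.2c tests each gene separately by chi-square. A reader of the results cannot tell in advance which one the conclusion on aim 4 follows.

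The timing adds weight. The definition of severe toxicity was revised in protocol version 6.0 (14 May 2024), and SAP item 14 places all analyses in May-June 2024.

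**Working it through.** **Inputs from the documents.** Alpha 0.05 and no correction (SAP item 16). Two-sided testing (protocol 8.1; the SAP gives no sidedness). Four TRAE contrasts (item 27.2c) and at least one PRO contrast (item 27.2e). Rates of 60% and 30% and 48 carriers per group (protocol 8.1 and Table 5).

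**Inputs assumed.** The documents give no gene-specific counts. The simulation takes 500 tested, 18-40 DPYD carriers, 40-90 UGT1A1 poor metabolizers, historical groups of equal size, and one common TRAE rate of 20-40%.

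**Step 1: the plan's own figure.** Exact two-sided Fisher power at 0.05 for 60% against 30% is 80.0% at 48 per group and 83.9% at 54. Table 5 states 80% and 83.9%. All 14 filled cells agree to within 2 percentage points. The protocol's alpha and power therefore belong to one two-sided test at 0.05 in pooled carriers.

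**Step 2: which tests belong to the aims.** Aim 4 has four TRAE tests and aim 5 has at least one PRO test, so 4 + 1 = 5.

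**Step 3: false-positive chance if the tests were independent and every null true.** The formula is 1 − (1 − 0.05)^k.

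| Tests | k | Chance of at least one p < 0.05 |
|---|---|---|
| One deciding contrast | 1 | 5.0% |
| Two historical TRAE contrasts | 2 | 1 − 0.95² = 9.75% |
| Four TRAE contrasts | 4 | 1 − 0.95⁴ = 18.5% |
| Four TRAE + one PRO | 5 | 1 − 0.95⁵ = 22.6% |

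Counting only errors that favour PGx (0.025 each), two historical tests give 1 − 0.975² = 4.9%, against 2.5% for one.

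**Step 4: allow for shared patients.** The within-cohort and historical tests of a gene use the same prospective carriers, so they are correlated. Simulating the four chi-square contrasts under the assumptions above gives about 9.5-11% for at least one of the two historical tests and about 16-17% for at least one of the four. For five tests, assumed correlations of 0.3, 0.5, 0.7 and 0.9 give 21%, 18%, 15% and 10%. The 22.6% is therefore the upper end for exactly five tests. More than one PRO test would raise it.

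**Step 5: the cost of control.** Fisher power at 48 per group, 60% against 30%, is 80.0% at 0.05 and 73.6% at 0.025.

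**The case against.** **Disclosure and context.** This is a non-randomised feasibility study. Its primary outcome is declared untested, the absence of correction is stated openly, and item 16 promises confidence intervals for the odds of severe TRAE. That stands, and it limits the seriousness. It does not tell a reader which result answers aim 4.

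**The deciding contrast is already named.** Protocol 4.1 and 8.1 and SAP item 7 fix the endpoint and the comparator, so it would be wrong to say the documents name nothing. The gap is narrower: item 27.2c splits the contrast by gene without a decision rule and omits the pooled version.

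**A larger count is tempting.** A reader might add four relative dose intensity tests and eight tests of treatment modification and discontinuation from item 29a ("These analyses were also performed for the UGT1A1 phenotype" doubles the last set), making 4 + 4 + 1 + 8 = 17. The false-positive chance would then be 58% if all were independent, or about 38-39% at an assumed correlation of 0.5. The documents do not support that as the error rate for the effectiveness aims. Item 8 limits those aims to TRAE and PRO, dose intensity is a separate secondary outcome, and item 29 is headed as additional analyses. Nine of the 17 are within-cohort comparisons (2 TRAE, 2 dose intensity, 1 PRO, 4 additional). A difference there cannot by itself show that testing improved outcomes, because no untested group is involved.

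**Disagreement between contrasts.** A reader might also treat a conflict between the within-cohort and historical results as a false-positive problem. It is not: carriers can do better than historical carriers and still worse than wild-type patients. The two questions differ, which is a reason to say which one decides.

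**The analyses are complete.** Naming a contrast now is after the fact. That is true and should be stated, but the choice can rest on protocol text that names the comparison and powers it.

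**Conclusion.** The point holds in a limited form. The SAP does not say which severe-TRAE contrast decides aim 4, applies no multiplicity control, and omits the pooled-carrier contrast behind the protocol's power calculation. The inflation is about twofold for the two historical tests (about 10%; about 5% against 2.5% in the favourable direction). It is just over threefold for the four TRAE tests (about 16-17%), and at most about 4.5-fold for the five aim-level tests (about 23%). These figures assume that every null is true. The 16-17% also rests on the assumed group sizes and event rates, and the 23% on independence and a single PRO test. The finding concerns secondary outcomes and does not touch the feasibility result.

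**What to change.** In SAP items 16 and 27.2c, name one contrast as deciding aim 4: severe TRAE in carriers of actionable genotypes, prospective against historical, at two-sided 0.05. This is the comparison powered in protocol 8.1. If a separate claim for each gene is wanted, test the DPYD and UGT1A1 historical contrasts by Holm (smaller p-value at 0.025, then the other at 0.05).

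Report the within-cohort TRAE tests and the dose intensity, PRO, modification and discontinuation tests as exploratory, with estimates and 95% confidence intervals and no claim of significance. State that this designation was made after the May-June 2024 analyses and follows the earlier protocol text.

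The cost is wording, plus one pooled test that item 27 does not now contain. Nominally significant secondary results could no longer be presented as demonstrated. The pooled test gives up no alpha. Under Holm's first step, power at 48 per group falls from 80.0% to 73.6%. That figure needs 48 carriers per group for each gene. With fewer it is lower: Table 5 gives 63.6% at 36 and 35.6% at 18 even at the full 0.05.

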
 1. To determine if chemotherapy-induced toxicity differs by ancestry group. 2. To determine the frequency of actionable DPYD and UGT1A1 in various ancestry groups. 3. To determine if PGx testing influences progression-free (PFS) and overall survival (OS). 4. To determine the cost-effectiveness of PGx guided chemotherapy dosing. 5. To determine the association of pre-treatment plasma uracil concentrations with severe (Grade 3 to 5) fluoropyrimidine induced toxicity with the first dose. 	
 1. The proportion of patients experiencing a serious treatment relate adverse event during the first six cycles of chemotherapy stratified by self-reported ancestry. 2. Minor allele frequency of variants in DPYD and UGT1A1 reported by self-reported ancestry. 3. PFS and OS in patients at 6 ± 2 months. 4. Means and variances of cost in the genotype-guided group as compared to the historical control group (Costs of hospitalizations, treatment, PGx test, medical services) 5. Pre-treatment plasma uracil concentrations as measured by HPLC.

OBJECTIVES	ENDPOINTS
Optional Microbiome Substudy at PCAM only	
1. To determine whether the microbiome composition impacts the occurrence of chemotherapy-induced adverse events	1. The change in bacterial abundance as measured by operational taxonomic units (OTUs) 2. The change in bacterial composition or beta diversity as measured by weighted UniFrac distance

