5.2 Exclusion Criteria

An individual who meets any of the following criteria will be excluded from participation in this study:

Exclusion criteria

1. Prior treatment with irinotecan
2. *DPYD* or *UGT1A1* genotype already known
3. Severe renal or hepatic impairment (or unacceptable laboratory values), including:
 - Neutrophil count of $<1.5 \times 10^9/L$, platelet count of $<100 \times 10^9/L$
 - Hepatic function as defined by serum bilirubin $>1.5 \times$ upper limit of normal (ULN), alanine aminotransferase (ALT), and aspartate aminotransferase (AST) $>2.5 \times$ ULN, or in case of liver metastases ALT and AST $>5 \times$ ULN
 - Renal function as defined by serum creatinine $>1.5 \times$ ULN, or creatinine clearance $<60 \text{ ml/min}$ (by Cockcroft-Gault Equation)
4. Women who are pregnant or breast feeding, or subjects who refuse to use reliable contraceptive methods throughout the study
5. Treating physician does not want subject to participate

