5.4 Participant recruitment

Approximately 1000 cases of GI cancer are treated annually at PCAM, 150 cases at PPMC, and 200 at LGH. Roughly 100 unique patients receive fluoropyrimidine and/or irinotecan-based chemotherapy regimen in a typical month at the PCAM GI cancer clinic. Based on the frequency of *DYPD* and *UGT1A1* variants and the number of GI cancer patients seen within Penn Medicine, we anticipate that testing 500-800 patients in this multisite study would result in 45-70 patients with the actionable genotypes (see Table 4). Approximately 20% of the GI cancer population at Penn Medicine is of African ancestry. All recruitment will be done through the Penn cancer centers and treating oncologists. Clinic schedules will be screened by the clinical research coordinator for new patients with GI cancer being evaluated for treatment. Prior to the scheduled visit, the research coordinator will notify the treating oncologist about potential eligible participants and remind them of the study. The treating oncologist will discuss the study with the patient during the evaluation visit and consent will be obtained by the treating GI oncology provider (physician or advanced practice provider) or the research coordinator. This will occur in person or by remote consent. Patients will be given a copy of the official informed consent form and an opportunity to ask questions. Patients will be given sufficient time to consider participating in the trial.

Participants who complete the patient questionnaire regarding attitudes towards PGx testing will receive a \$25 gift card. The Greenphire ClinCard will be used to disburse funds and mailed to the patient.

Women of childbearing potential who are pregnant or breastfeeding will not be recruited into this study due to the risk of fetal harm caused by exposure to 5-FU, capecitabine, or irinotecan and the potential for serious adverse reactions in breastfed infants. A pregnancy test is not routinely performed in these patients at Penn Medicine thus will not be included as a study procedure.

Table 4. Anticipated study initiation and estimated participant accrual across sites

Calendar year	Q1 2021	Q2 2021	Q3 2021	Q4 2021	Q1 2022	Site totals
Site						
PCAM (20/mo)	60	60	60	60		240
PPMC (10/mo)		30	30	30	30	120
LGH (20/mo)		60	60	60	60	240
Total						600

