Adherence and protocol deviations	17	
 Removal of inclusion criteria of ECOG status, patients with higher ECOG status (3 or 4) still suitable for treatment with fluoropyrimidines. Oncologist will determine suitability for treatment with fluoropyrimidines on a case-by-case basis. Removal of inclusion criteria of prior treatment of fluoropyrimidines, physicians have expressed interest in obtaining genotype information regardless of a patient's prior treatment status, and particularly for individuals with previous intolerance of fluoropyrimidine to guide future treatment decisions. Participants that received the PGx test after initiation of chemotherapy, due to requests by the treating oncologist, were not included as part of the primary analysis and were reported/described separately and noted as protocol deviations. Updated timeframe for endpoint collection, feasibility endpoint time frame revised from '7 days' to 'prior to the first dose of chemotherapy'. Seven days is less clinically relevant than patient-specific treatment schedules. adverse event data and PRO questionnaires to be collected over first six cycles, not months. It is not necessary to collect AE data over the longer time period for study purposes given that chemotherapy toxicity is typically experienced during initial cycles. Prospective completion of chemotherapy related toxicity per the National Cancer Institute-Common Terminology Criteria for Adverse Events (NCI-CTCAE) was not feasible due to a lack of a consistent research coordinator throughout the study. In addition, the completion rate for the PROs was very low (22%) therefore we could not assign a grade to the adverse event. Revised definition severe toxicities from \geq Grade 3 toxicities to treatment related adverse events requiring treatment in the hospital, emergency department, or oncology evaluation center.

Analysis population	18	Modified intent to treat, removing participants that did not meet the inclusion criteria (i.e., received PGx test after chemotherapy or did not receive qualifying chemotherapy agent).
---------------------	----	---

Section 5: Trial population

Section	Index	Description

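### Fluoropyrimidine-pretreated patients are eligible since v4.0, but no SAP analysis of DPYD outcomes separates or adjusts for them, so selection bias of unknown direction is possible

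*Combined protocol and SAP*

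**What the plan says.** **Eligibility.** Protocol 5.1 and 5.2 and SAP item 22 contain no fluoropyrimidine-naive requirement. The only prior-treatment exclusion is "Prior treatment with irinotecan", so the gap concerns DPYD. The naive criterion was removed in v4.0 (10 November 2021). SAP item 17 gives the reason: interest in the genotype regardless of prior treatment, "particularly for individuals with previous intolerance of fluoropyrimidine to guide future treatment decisions".

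**Recruitment.** Protocol 5.4: "Clinic schedules will be screened by the clinical research coordinator for new patients with GI cancer being evaluated for treatment".

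**Analysis set.** SAP item 17 keeps participants tested after chemotherapy had started, at the oncologist's request, out of the primary analysis and describes them separately as deviations. Item 18 removes participants who failed the inclusion criteria, giving two cases: testing after chemotherapy, or no qualifying drug received. Neither item mentions an earlier course.

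**Analyses.** SAP item 27.2c compares TRAE proportions by chi-square, both DPYD carriers against wild-type and prospective against historical carriers. It adds a "multivariable logistic regression model adjusting for age, sex, race, tumor type, ECOG score, presence of metastases, intent of treatment, DPYD phenotype"; the only further covariate is UGT1A1 phenotype, and selection is stepwise. Item 27.2d compares RDI by t-test. Item 29a compares modifications and discontinuations by chi-square. Protocol 8.2.2 had adjusted RDI and patient-reported outcomes for line of therapy; the SAP does not.

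**Allele frequencies.** A tertiary endpoint in protocol section 3 is "Minor allele frequency of variants in DPYD and UGT1A1 reported by self-reported ancestry". The SAP does not list it, and no analysis population is set for it.

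**Data.** Previous cancer treatments and number of lines are baseline items (protocol 7.4, SAP item 25), recorded if available in the chart. Footnote 2 of the Schedule of Activities adds ongoing toxicities from earlier therapy.

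**The concern.** The effectiveness hypothesis in protocol 8.1 contrasts carriers on full dose with carriers on genotype-guided dose, and the endpoints are framed around the first dose and first six cycles. A pretreated carrier fits this contrast poorly. One who reacted badly before may be treated in the light of that history whatever the genotype shows. One who tolerated an earlier course has already been selected for lower risk. SAP item 17 itself says that toxicity typically appears in the initial cycles, so first exposure and re-exposure need not carry the same risk.

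If such patients are pooled with first-exposure patients, a difference from the historical controls may partly reflect prior exposure rather than genotype guidance. Selection on past tolerance or intolerance also changes the carrier fraction, so the allele frequencies may not describe GI cancer patients starting a fluoropyrimidine. No section defines prior exposure for the Penn Medicine Biobank (PMBB) controls, so nothing ensures that the two cohorts are alike in this respect.

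**Working it through.** **1. The plan's own figure.** Protocol 8.1 assumes severe TRAEs will "decrease from 60% in the variant carriers receiving full dose chemotherapy in the historical control group" "to 30% in variant carriers receiving genotype guided chemotherapy", with power "based on two-sided Fisher's exact test at the alpha level of 0.05". Exact enumeration of the two-sided Fisher test at 60% vs 30% with 48 per group gives 80.0%, as in Table 5. The other Table 5 cells also reproduce within one percentage point. The power table is not in dispute. Its 48 counts carriers of actionable variants in either gene; a DPYD-only group would be smaller.

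**2. Exposure to the change.** From 10 November 2021 to 31 December 2022 is 416 days; from 1 March 2021 to 31 December 2022 is 670 days. 416/670 = 62% of the calendar window follows v4.0. Accrual by period is not given.

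**3. Base DPYD carrier prevalence (Table 1, no-function and decreased-function alleles, HapB3 counted once).**
- European ancestry: allele frequencies sum to 0.0372; 1 − (1 − 0.0372)² = 7.3%.
- African ancestry: sum 0.021; 1 − (1 − 0.021)² = 4.2%.
- With 20% African ancestry (protocol 5.4), and European frequencies assumed for the rest: 0.8 × 7.3% + 0.2 × 4.2% = 6.7%.

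**4. Prevalence given past tolerance or intolerance.** Assumed severe toxicity is 60% in carriers (protocol 8.1, stated there for actionable variants of either gene) and 30% in non-carriers (the upper figure for all patients in protocol 2.2).
- Intolerant: 0.067 × 0.6 / (0.067 × 0.6 + 0.933 × 0.3) = 0.0402/0.3201 = 12.6%.
- Tolerant: 0.067 × 0.4 / (0.067 × 0.4 + 0.933 × 0.7) = 0.0268/0.6799 = 3.9%.

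**5. Pooled prevalence** = (1 − f) × 6.7% + f × (prevalence in the pretreated). The pretreated share f is not given and is assumed.

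| f | All pretreated tolerant | Intolerant share 32% | All pretreated intolerant |
|---|---|---|---|
| 10% | 6.4% | 6.7% | 7.3% |
| 30% | 5.9% | 6.7% | 8.5% |

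The neutral share of 32% is the denominator 0.3201 in step 4: the proportion with severe toxicity in an unselected cohort.

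**6. TRAE rate in PGx carriers** = (1 − g) × 30% + g × r. Here g is the pretreated share of PGx carriers and r their TRAE rate (both assumed). Controls are held at 60%, with 48 per group.

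| g | r | Pooled rate | Difference from 60% | Power |
|---|---|---|---|---|
| 10% | 15% | 28.5% | 31.5 points | 84% |
| 10% | 30% | 30% | 30 points | 80% |
| 10% | 60% | 33% | 27 points | 70% |
| 30% | 15% | 25.5% | 34.5 points | 91% |
| 30% | 30% | 30% | 30 points | 80% |
| 30% | 60% | 39% | 21 points | 47% |

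**7. Cost of a first-exposure comparison (60% vs 30%).** Removing 10%, 20% or 30% of 48 PGx carriers leaves 43, 38 or 34. Against 48 controls, power is 78.6%, 75.9% and 76.2% (the last step is not monotone because the test is discrete). If controls shrink equally, power is 73.7% at 43 per group and 62.2% at 34 per group.

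**The case against.** The strongest reply is that items 17 and 18 already deal with this. They set aside patients tested once chemotherapy had begun, which probably covers some tests prompted by a reaction. Read literally, item 18's reference to testing after chemotherapy could cover any earlier course. That stands as an ambiguity, not as an answer. Item 17 treats the dropped criterion and late testing as separate matters. Item 18 removes people who fail the inclusion criteria, and pretreated patients now meet them. Counting earlier courses would undo the amendment for analysis.

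A reader might infer from the stated reason for v4.0, together with screening aimed at new patients, that pretreated patients entered mainly because of past toxicity and that carrier frequency is therefore inflated. The documents do not support this. Interest in intolerant patients is a motive for the change, not a count of who enrolled. A new patient being evaluated for treatment need not be untreated, as the baseline items on earlier treatments and lines show. Patients who tolerated earlier therapy would push prevalence down.

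Other points also stand. At 600 participants (Table 4), the standard error of a 6.7% prevalence is √(0.067 × 0.933/600) = 1.0 percentage point, so the shifts at f = 10% (−0.3 to +0.6 points) lie within sampling error. Presence of metastases and treatment intent in the TRAE model may partly stand in for line of therapy. If PMBB controls had similar prior exposure, the imbalance would be smaller. The endpoints affected are secondary and tertiary; the primary aim is implementation.

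**Conclusion.** The concern holds as a risk of selection bias and confounding whose direction and size the documents do not determine. It is established that pretreated patients, including those with prior intolerance, are eligible, and that no SAP comparison of DPYD TRAE, RDI, or modifications and discontinuations stratifies, adjusts or excludes on prior fluoropyrimidine exposure. The protocol's line-of-therapy adjustment for RDI was not carried into the SAP.

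It is not established that bias occurred, or which way it runs. With 10% to 30% pretreated, DPYD carrier prevalence could lie between 5.9% and 8.5% instead of 6.7%, and the TRAE rate in PGx carriers between 25.5% and 39% instead of 30%. Prevalence does not shift if the pretreated are unselected, and the TRAE rate does not shift if their risk is the same. These ranges rest on the assumed shares, the assumed TRAE rates of 15% to 60%, and toxicity figures borrowed from protocol 2.2 and 8.1. Feasibility and fidelity are not called into question. The change should be made because at least part of it uses data already collected.

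**What to change.** 1. State in SAP item 18 that testing after chemotherapy refers to the current course.
2. Add prior fluoropyrimidine exposure (or, failing that, line of therapy) to the TRAE model in item 27.2c as a forced term, outside the stepwise selection.
3. Repeat the DPYD comparisons of TRAE, RDI, and modifications and discontinuations (items 27.2c, 27.2d and 29a), and the protocol's allele frequencies by ancestry, in fluoropyrimidine-naive patients.
4. Report pretreated patients separately, with counts by prior intolerance.
5. Apply the same definition of prior exposure to PMBB controls where their records allow, and say so where they do not.
6. Keep pretreated patients in the feasibility and fidelity endpoints.

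**Cost.** The first-exposure comparison has fewer carriers: power is about 76% to 79% instead of 80% if 10% to 30% of the PGx carriers are removed and 48 controls remain, and about 74% to 62% if controls shrink equally. SAP item 14 places all analyses in May and June 2024, so this means some re-analysis, to be labelled post hoc, as well as new wording. Prior treatment is already a baseline item for participants, if available in the chart. Resolved past intolerance, and prior exposure in controls, may need chart abstraction; the documents do not show that control records allow it.
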